5.7. Overview of scoring of liver biopsies

Liver biopsies will be obtained from each patient in the 6 months prior to randomization and after 96 weeks of treatment. Standard of care baseline liver biopsies will be reviewed and scored by the local NASH CRN pathologist to determine eligibility. Standard of care slides accessed with patient's permission and shipped to the Histology Review Center will be scored by central review of the slides by the Pathology Committee. TONIC trial follow-up liver biopsy slides will be reviewed and scored by the local NASH CRN pathologist first for patient care (data not collected) and then shipped to the Histology Review Center for scoring by central review of the slides by the Pathology Committee.

The tissue will be examined by light microscopy and scored based upon the NASH CRN NAFLD/NASH scoring system. The scoring system is detailed in the Liver Biopsy Procedure and NAFLD/NASH Histologic Scoring System Manual prepared by the NASH CRN Pathology Committee and approved by the NASH CRN Steering Committee. Pediatric and adult biopsies will be scored according to the same criteria. However, since change in histology is not the primary outcome for TONIC trial and since children may show a different pattern of progression than adults, criteria for improved histology in children will not be specified at this time. Briefly, biopsies will be assessed for the following:

- (1) Adequacy of the biopsy sample for reading;
- (2) Steatosis (including grade of 0-3, location, and whether microvesicular);

- (3) Fibrosis based upon Masson's trichrome stain as 0-4 with:
 0 = none
 1a = mild zone 3 perisinusoidal
 1b = moderate zone 3 perisinusoidal
 1c = portal/periportal only
 2 = zone 3 and periportal
 3 = bridging
 4 = cirrhosis
- (4) Lobular inflammation as 0, 1 (<2 areas seen), 2 (2-4 areas seen), or 3 (>4 areas seen under 20-fold magnification) and as presence or absence of microgranulomas and lipogranulomas
- (5) Portal inflammation as 0 (none), 1 (mild), or 2 (greater than mild)
- (6) Liver cell injury: Ballooning as 0 (none), 1 (few) and 2 (many), with notation of presence or absence of acidophilic bodies (0 = rare or 1 = many), pigmented macrophages (0 = rare/absent, 1 = many), and megamitochondria (0 = rare/absent, 1 = many)
- (7) Mallory bodies as 0 (rare/absent) or 1 (many)
- (8) Glycogen nuclei as 0 (rare/absent) or 1 (many)

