7.1. Hypotheses

Primary hypotheses:

- In pediatric nondiabetic patients with NAFLD, improvement in insulin resistance over 96 weeks of treatment with metformin will result in sustained reduction in serum alanine aminotransferase (ALT) compared to treatment with placebo
- In pediatric nondiabetic patients with NAFLD, improvement in oxidative stress status over 96 weeks of treatment with vitamin E will result in sustained reduction in serum ALT compared to treatment with placebo

Secondary hypotheses:

- Treatment with metformin or vitamin E will result in sustained reduction in serum AST and GGT compared to treatment with placebo
- Metformin and vitamin E are equally effective in achieving histologic improvement in nondiabetic children with NAFLD
- Levels of proinflammatory cytokines and serum markers for fibrosis will decrease with treatment with metformin and with vitamin E compared to treatment with placebo
- Pediatric nondiabetic patients with NAFLD have an impaired quality of life, and these scores will improve as their serum ALT improves upon treatment with metformin or vitamin E compared to treatment with placebo

Other questions to be addressed:

- We predict that insulin resistance is common in pediatric nondiabetic patients with NAFLD and will be significantly related to waist-to-hip ratio, waist circumference, serum ALT, and hepatic histology
- We predict that degree of obesity will be significantly related to hepatic histology in pediatric nondiabetic patients with NAFLD and more severe obesity (BMI or BMI z score) will be related to greater elevations in ALT and more advanced hepatic histology

- We predict that serum markers for steatosis, inflammation, and fibrosis will be significantly related to hepatic histology in pediatric nondiabetic patients with NAFLD
- We predict that worsening hepatic histology will be significantly related to a worsening in health-related quality of life in pediatric nondiabetic patients with NAFLD and more advanced histology will have worse health-related quality of life as measured by scores on the PedsQL
- We predict that improvement in the measures of insulin resistance will be significantly related to improvements in liver histology, serum ALT, and serum markers for steatosis, inflammation, and fibrosis in pediatric nondiabetic patients with NAFLD
- We predict that therapy with vitamin E will improve insulin resistance in pediatric nondiabetic patients with NAFLD

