7.3. Statistical analysis

Primary hypotheses:

Statistical analyses for the two primary hypotheses will follow the intention-to-treat paradigm, which means that all randomized patients with baseline and 96 week serum ALT values will be analyzed in the treatment group to which they were assigned. Any randomized patient who does not have the requisite ALT values will be accounted for and compared by assigned treatment group. Patients not able to be included in the intention-to-treat analyses will be compared to those who are included with respect to demographic and other characteristics.

Since the primary outcome measure, defined in Section 7.2, is a binary indicator of sustained reduction in ALT after 96 weeks of treatment compared to baseline and since the randomization is stratified by clinic, P-values for the primary hypotheses will be derived from the Mantel-Haenszel χ^2 test for stratified 2x2 tables⁴⁴. Two P-values will be derived: one comparing proportions improved in the group assigned to metformin compared to the group assigned to placebo and another comparing the group assigned to vitamin E to the group assigned to placebo. Since two primary comparisons are planned, a P-value of 0.025 will be considered significant, applying a Bonferroni correction for multiple comparisons.

Given the randomized design and adequate size planned for the TONIC trial, it is unlikely that confounding of the treatment groups by covariates related to the change in serum ALT will occur. However, if confounding should occur, logistic regression analyses with sustained reduction in ALT as the binary response and treatment group indicators and any suspected confounders as covariates will be carried out to determine the sensitivity of the primary P-values to confounding.

Secondary hypotheses:

Statistical analyses for the first secondary hypothesis, that treatment with metformin or vitamin E will result in sustained reduction in serum AST and GGT compared to treatment with placebo, will be the same as described for primary hypotheses.

The second secondary hypothesis, that metformin and vitamin E are equally effective in achieving histologic improvement in nondiabetic children with NAFLD, involves the histologic outcome measure. Equivalence will be assessed by means of 95% confidence intervals on the difference in proportions improved.

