7.5. Justification of sample size

The planned sample size for the TONIC trial is 180 patients with equal allocation to each of the three treatment groups (60 per group).

We based the sample size estimates on a two-group, binomial comparison of the proportions of patients satisfying the primary outcome, reduction in serum ALT to either 50% of the baseline value OR to 40 U/L or lower which is sustained for at least one year (defined in Section 7.2) over the 96 week course of treatment. Since TONIC is a three group trial with two primary hypotheses, we assume that the two primary comparisons, metformin vs. placebo and vitamin E vs. placebo, require the same sample size and reduce the type I error from 0.05 to 0.025 (Bonferroni correction). Expected proportions improved were approximated using pilot data from a 48-week metformin study ([name], personal communication) and from a consensus among our investigators as to the response in the placebo group. Currently, there are no available data to estimate the response in vitamin E, which is assumed, for purposes of planning the trial, to be the same as for metformin.

The sample size calculations were performed using the PS⁴⁵ software using the formula:

$$n = \frac{\left[z_{1-\alpha/2} \sqrt{2\bar{\pi}(1-\bar{\pi})} + z_{1-\beta} \sqrt{\pi_1(1-\pi_1) + \pi_2(1-\pi_2)} \right]^2}{(\pi_1 - \pi_2)^2}$$

where,

n = sample size per group

π_1 = expected proportion improved in placebo group (assumed=0.20)

π_2 = expected proportion improved in metformin or vitamin E group (0.50)

$\bar{\pi}$ = average of π_1 and π_2

α = Two-sided type I error (0.025, Bonferroni corrected for two comparisons)

β = Type II error (0.10; ie, 90% power)

The number per group, using the above formula is 60 patients; or a total of 180 for the trial. As indicated in Section 7.4, patients with missing primary outcome data will be considered unimproved and will be included in the 180 patients.

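### The metformin versus vitamin E equivalence hypothesis on histology has no margin or decision rule, and the trial's size would support only a margin of about 24 to 31 points

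*Supplement*

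**What the plan says.** The second of the secondary hypotheses in section 7.1 reads "Metformin and vitamin E are equally effective in achieving histologic improvement in nondiabetic children with NAFLD". Section 7.3 treats it as a question of equivalence and gives one sentence of method: "Equivalence will be assessed by means of 95% confidence intervals on the difference in proportions improved". Neither section, nor any other part of the protocol, names an equivalence margin or says what interval would support or refute the hypothesis.

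The size comes from section 7.5: "We based the sample size estimates on a two-group, binomial comparison of the proportions of patients satisfying the primary outcome". The calculation compares each active group with placebo on ALT. The metformin versus vitamin E comparison on histology has no size or power statement.

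The response is not pinned down either. Section 5.7 says that "criteria for improved histology in children will not be specified at this time". Section 7.2 does define improvement, as any improvement in the NAS and in specific feature scores, but does not say which of these proportions the equivalence sentence refers to.

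Section 7.3 also says that secondary hypotheses will generally be analysed as three comparisons (each drug against placebo, and drug against drug), without adjustment for multiplicity.

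**The concern.** A confidence interval supports equivalence only if it lies wholly inside a margin fixed in advance. Without a margin, the one reference value left to a reader is zero, and an interval that covers zero shows only that a difference was not detected. At stake is whether the trial may report the two drugs as equally effective on liver histology.

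Had the trial been large enough, this would be one omitted number. The question is therefore whether an interval from about 60 children per arm could fit inside a margin that anyone would accept.

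**Working it through.** **Inputs.** 60 per group (section 7.5). Missing data of no more than 10% (section 7.4), so about 54 per arm if children without a week-96 biopsy are left out; section 7.4 counts missing as unimproved for the primary outcome only. Planned ALT rates of 0.20 on placebo and 0.50 on active drug, with alpha and power given as "Two-sided type I error (0.025, Bonferroni corrected for two comparisons") and "Type II error (0.10; ie, 90% power") in section 7.5. The histologic response rate is not in the documents; I assume it equal in both drug arms and show 20% to 50%. The value 50% is the ALT planning rate and gives the largest variance.

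**The plan's own figure.** With z(0.9875) = 2.2414, z(0.90) = 1.2816 and mean proportion 0.35, the printed formula gives

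n = [2.2414·√(2·0.35·0.65) + 1.2816·√(0.20·0.80 + 0.50·0.50)]² / 0.30² = 60.45.

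This agrees with the stated 60; power at 60 per group is 89.8%.

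**Width and margin for metformin minus vitamin E.** With common true rate p and n per arm:

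- SE = √(2p(1−p)/n)
- 95% half-width = 1.96·SE
- margin met with 80% power when the true difference is zero = (1.96 + 1.2816)·SE

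At p = 0.50 and n = 60: SE = √(0.50/60) = 0.0913, half-width 0.179, margin 3.2416·0.0913 = 0.296.

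| True rate | Half-width, 60 per arm | Half-width, 54 per arm | 80%-power margin, 60 per arm | 80%-power margin, 54 per arm |
|---|---|---|---|---|
| 20% | 14.3 | 15.1 | 23.7 | 25.0 |
| 30% | 16.4 | 17.3 | 27.1 | 28.6 |
| 40% | 17.5 | 18.5 | 29.0 | 30.6 |
| 50% | 17.9 | 18.9 | 29.6 | 31.2 |

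(All in percentage points.)

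**Chance that the whole interval lies inside ±m when the drugs are identical**, by 2Φ(m/SE − 1.96) − 1, or zero if that is negative, at a 50% rate. Exact binomial values are in brackets.

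| Margin | 60 per arm | 54 per arm |
|---|---|---|
| ±15 | 0% | 0% |
| ±20 | 18% (22%) | 9% (8%) |
| ±25 | 56% (59%) | 48% (50%) |
| ±30 | 82% (83%) | 75% (79%) |

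At a 20% rate with 60 per arm, the normal-approximation figures are 7% for ±15, 56% for ±20 and 86% for ±25.

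**Size needed** for 80% power, n = 2p(1−p)·3.2416²/m², for rates of 30% to 50%: 111 to 132 per arm for ±20, 197 to 234 for ±15, and 442 to 526 for ±10.

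**If the interval were read against zero instead.** Exact enumeration of the Wald 95% interval with 60 per arm gives the chance that it covers zero: 79% at true rates of 50% and 40%, 61% at 50% and 35%, 38% at 50% and 30%, and 5% at 50% and 20%.

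**The case against.** Several points on the other side stand.

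- A reader might infer that the plan declares equivalence whenever the interval covers zero. No such rule is written. Section 7.3 says only that the interval will be used, and judging it by its width is also open. The misreading is a risk left by silence.
- A reader might infer that two ineffective drugs would pass unnoticed. Section 7.3 already plans each drug against placebo beside the head-to-head comparison, so such a result would be visible. The plan does not, however, make benefit over placebo a condition of the equivalence conclusion.
- A reader might infer that a much better drug would probably be called equivalent. The figures do not support this: at a 30-point gap (50% and 20%) the interval covers zero in about 5% of trials. The risk lies with gaps of 10 to 15 points, at 79% and 61%.
- A reader might infer that no margin under 30 points can be met. That is too absolute. At a 50% rate with 60 per arm, ±25 would be met slightly more often than not, and at a 20% rate the 80%-power margin is about 24 points.
- Equivalence is often judged by a 90% interval. That would lower the 80%-power margin only to about 25 to 27 points (rates 30% to 50%, 60 per arm).
- This is one unadjusted secondary hypothesis, and section 7.3 already produces most of what an estimation approach needs.

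What remains is a stated equivalence hypothesis with no margin or decision rule, at a size never chosen for it.

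**Conclusion.** The concern holds as a fault of one secondary hypothesis. At 54 to 60 biopsies per arm and equal true rates of 20% to 50%, the 95% half-width is about 14 to 19 points and the margin met with 80% power about 24 to 31 points. The ALT effect assumed for planning is 0.50 − 0.20 = 30 points, so such a margin could count as equivalent two drugs that differ by nearly as much as an active drug was expected to differ from placebo. At a 50% rate there is no chance of meeting ±15 points and a 9% to 18% chance of meeting ±20 (normal approximation).

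The result rests on the assumed histologic rate, on equal true rates, and on no more than 10% of biopsies missing. More missing biopsies would widen the interval. The documents do not support saying that the hypothesis is impossible to support, or that false equivalence is likely when the drugs differ greatly. The primary analysis and its sample size are not affected.

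**What to change.** In section 7.1, delete the equal-effectiveness hypothesis, or restate it as the aim of estimating how the two drugs differ on histology. In section 7.3, replace the equivalence sentence with text such as: the difference in the proportion with histologic improvement (any improvement in the NAS, as defined in section 7.2), metformin minus vitamin E, will be reported with its 95% confidence interval and read alongside each drug against placebo; no conclusion of equivalence will be drawn. Naming the NAS response also settles which proportion is meant, which sections 5.7 and 7.2 leave open.

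The cost is wording in two sections, with no added patients, visits or data. The sponsor gives up a secondary equivalence claim that the design has little ability to support.

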3.2. Treatment groups

Patients who have signed an informed consent statement and who meet the eligibility criteria will be randomly assigned to one of three groups for 96 weeks of treatment:

- Metformin (500 mg b.i.d.) and vitamin E-placebo (b.i.d)
- Vitamin E (400 IU, natural form, b.i.d.) and metformin-placebo (b.i.d.)
- Metformin-placebo (b.i.d.) and vitamin E-placebo (b.i.d.)

The randomization scheme will assign patients in randomly permuted blocks of assignments stratified by clinical center; block size will be determined randomly. This scheme will ensure that the three groups will be balanced by calendar time of enrollment (to minimize secular effects) and by clinic (to minimize clinic-specific effects of differences in patient populations and management).

The randomization plan will be prepared and administered centrally by the Data Coordinating Center (DCC) but will not require real time interaction with a DCC staff member. Requests for randomizations will be made by the clinics using a web-based application. An assignment will be issued only if the data system shows that the patient is eligible, has signed the consent statement, and has had all required baseline data keyed to the database.

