Analyses for outcomes related to other secondary hypotheses will be conducted in two ways. Improvement will be analyzed both as a binary outcome (improved vs. not improved) and also in terms of the numerical change in the outcome. Binary outcomes will be compared using the Mantel-Haenszel χ^2 test for stratified 2x2 tables. Numerical changes will be analyzed by descriptively comparing the between-treatment group differences in mean and median changes; P-values will be derived from Wilcoxon rank sum tests for comparison of the distribution of changes in each group. If concerns about confounding arise, logistic regression models for improvement outcomes and linear regression models for numerical change outcomes will be used to correct for the confounding. Analyses for secondary hypotheses will generally involve three separate analyses, one for each treatment group comparison: metformin vs. placebo, vitamin E vs. placebo, and metformin vs. vitamin E. No adjustments for multiple comparisons will be applied to the secondary hypotheses; however, any significant findings must be interpreted taking into account the strength of the finding and its biologic plausibility.

Other questions to be addressed:

A series of other questions of interest were listed in Section 7.1. Analyses related to these questions will involve a mix of appropriate exploratory and confirmatory analyses, similar, but not limited to those described for the primary and secondary hypotheses.

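### Numerical secondary outcomes are tested by an unstratified Wilcoxon test on change from baseline; a pre-specified model with baseline and clinic would usually be more precise, at little cost

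*Supplement*

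**What the plan says.** Section 7.3 of the protocol treats two kinds of secondary outcome differently in the same paragraph. For improvement yes/no it says "Binary outcomes will be compared using the Mantel-Haenszel" chi-squared test for stratified tables. For numerical changes, differences in means and medians are descriptive only, and "P-values will be derived from Wilcoxon rank sum tests for comparison of the distribution of changes in each group". No strata are mentioned for that second test.

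The reason given for stratifying the primary test is the design: "since the randomization is stratified by clinic, P-values for the primary hypotheses will be derived from the Mantel-Haenszel" test. Section 3.2 confirms it: "The randomization scheme will assign patients in randomly permuted blocks of assignments stratified by clinical center".

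Regression is conditional: "If concerns about confounding arise, logistic regression models for improvement outcomes and linear regression models for numerical change outcomes will be used". The primary outcome has a similar trigger: "if confounding should occur, logistic regression analyses with sustained reduction in ALT as the binary response". Neither sentence gives a criterion for acting or a covariate list, and neither names the baseline value. The regression models in section 7.4 do not fill the gap, because they apply only if missing data exceed 10% and also differ by group.

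On scope, section 7.1 lists four secondary hypotheses. Section 7.3 sends AST/GGT to the primary method and the histology hypothesis to confidence intervals on proportions improved. The Wilcoxon sentence therefore directly governs the other two: cytokine and fibrosis markers, and quality of life. It reaches further numerical outcomes only because the section's other questions are to be analysed along similar lines, without being confined to those methods.

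**The concern.** A change score subtracts the baseline value with a fixed coefficient of one. Unless the follow-up value really moves one-for-one with baseline, this leaves avoidable baseline noise in the comparison. Regressing the week-96 value on treatment and baseline lets the data set the coefficient, which in large samples cannot be worse and is usually better. Baseline PedsQL and banked baseline serum are already collected at screening visit 2.

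Two further points follow. The plan's own reason for stratifying the binary tests applies equally to the numerical ones, so the two are inconsistent. And when adjustment depends on a judgement that confounding has arisen, both the decision and the covariates are open until the data are seen. Section 7.3 plans three pairwise comparisons per secondary outcome with no multiplicity adjustment, so that freedom is better removed. The sample size was set for the binary ALT outcome alone, so the numerical outcomes have no stated power.

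**Working it through.** **The plan's own figure.** Section 7.5 uses proportions 0.20 and 0.50, two-sided alpha 0.025 and 90% power. With mean proportion 0.35:

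n = [2.2414 × √(2 × 0.35 × 0.65) + 1.2816 × √(0.16 + 0.25)]² / 0.30² = 60.45

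The stated 60 per group is reproduced (61 if rounded up; power at 60 is 89.8%). It concerns only the primary outcome and is not affected by this point.

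**Variance comparison.** The documents give no SD or correlation for the numerical outcomes, so both are assumptions. With SD s0 at baseline, s1 at week 96 and correlation r within arm:

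- Var(change) = s0² + s1² − 2·r·s0·s1
- Var(ANCOVA) = s1²(1 − r²)
- Difference = (s0 − r·s1)², which is never negative

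With s0 = s1 = s, these are 2s²(1 − r) and s²(1 − r²), and their ratio is (1 + r)/2.

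| r (assumed) | Var(change)/s² | Var(ANCOVA)/s² | Ratio | 60 per group on change is worth | Per group on change to match ANCOVA at 60 |
|---|---|---|---|---|---|
| 0.3 | 1.40 | 0.91 | 0.65 | 39 | 92 |
| 0.5 | 1.00 | 0.75 | 0.75 | 45 | 80 |
| 0.7 | 0.60 | 0.51 | 0.85 | 51 | 71 |
| 0.9 | 0.20 | 0.19 | 0.95 | 57 | 63 |

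**Unequal SDs.** Take r = 0.8, s0 = 1, s1 = 1.25. Var(change) = 1 + 1.5625 − 2.0 = 0.5625, and Var(ANCOVA) = 1.5625 × 0.36 = 0.5625, so there is no gain. If the SD shrinks instead, to s1 = 0.8, the figures are 1 + 0.64 − 1.28 = 0.36 and 0.64 × 0.36 = 0.2304, a ratio of 0.64. With equal SDs at r = 0.8 the ratio is 0.90.

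**The planned test itself.** The formula compares ANCOVA with a mean-change test, not with a Wilcoxon. A simulation was therefore run with normal data, two arms of 60, eight clinics, two-sided 0.05, an effect of 0.5 residual SD and 2,000 runs per setting (Monte Carlo standard error at most √(0.25/2000), about 1 point). With no clinic effect, power of the Wilcoxon on change against ANCOVA was:

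- r = 0.3: 56% against 79%
- r = 0.5: 64% against 78%
- r = 0.7: 69% against 77%
- r = 0.9: 74% against 78%

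Part of each gap is the rank test's own modest loss when data are exactly normal.

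**Validity.** With no treatment effect and an assumed clinic intraclass correlation of 0.10 (3,000 runs), the planned Wilcoxon rejected in 3.9% of runs at r = 0.5 and 4.3% at r = 0.7.

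**Clinic.** With intraclass correlation 0.10, adding clinic to ANCOVA gained 2 to 3 points of power. Stratifying the Wilcoxon by clinic (van Elteren) changed power by 0 to about +1 point. With no clinic effect, van Elteren lost about 2 to 3 points.

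**The case against.** The strongest reply is that nothing here is an error. A rank test on change is valid, suits skewed markers and bounded scores, and applies to secondary outcomes that section 7.3 already says must be interpreted with care. No separate analysis plan is shown, and covariate lists are commonly left to one. Most of this stands, and it limits the weight of the point. It does not remove it: the protocol does state a method, and a usually more precise one is available from data already collected.

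Several stronger readings are tempting but unsupported:

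- A reader might infer that the planned test is biased by regression to the mean. Under randomization that acts equally on the arms in expectation, and the simulated type I error was not inflated.
- A reader might infer that baseline is ignored. It is subtracted; what is missing is conditioning on it.
- A reader might turn the ratios 0.65 to 0.85 into a free gain worth 54% to 18% more patients (2/(1 + r) − 1 at r = 0.3 to 0.7). That needs equal SDs and a mean-change comparator, and at r = 0.9 it is 5%. In growing children some SDs may well change over 96 weeks.
- A reader might count the missing clinic strata as lost precision. The simulation shows almost none; this is an inconsistency with the design and the binary tests.
- A reader might extend the rule to every numerical outcome in section 7.2. The text ties it directly only to cytokine and fibrosis markers and PedsQL.
- A reader might think the primary result is at risk. It rests on a clinic-stratified test, and the logistic model is only a check on it.

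**Conclusion.** The point holds as one of efficiency and pre-specification for numerical secondary outcomes. With equal SDs and roughly normal data, testing change costs about 35%, 25%, 15% or 5% of the effective sample size at assumed r of 0.3, 0.5, 0.7 or 0.9. In the simulation this was roughly 23 down to 4 points of power, including the rank test's own loss under normality. The direction (no large-sample loss from conditioning on baseline) does not depend on equal SDs, but the size does, and it can be zero. For skewed or ordinal outcomes the figures are illustrative only. Clinic adjustment is justified by consistency with the randomization, not by precision. The conclusions on the primary outcome, its alpha and the sample size stand as planned.

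**What to change.** In section 7.3, pre-specify for numerical secondary outcomes a linear model of the week-96 value on treatment, baseline value and clinic. Use the log scale for skewed markers and a rank-based version with the same covariates for ordinal scores. Report the adjusted difference and its 95% CI for each of the three pairwise comparisons, list the outcomes covered, and keep the Wilcoxon test on change as a sensitivity analysis. Remove the confounding trigger for these outcomes.

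Optionally, replace the similar trigger for the primary outcome with one named supportive logistic model containing treatment, log baseline ALT and clinic. Baseline ALT is a natural covariate because the response threshold depends on it: a child entering at 61 U/L qualifies with a fall to 40 U/L, which is 21/61 = 34%, whereas a child at 80 U/L or above needs 50%. The Mantel-Haenszel test remains primary.

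The cost is a change of wording, some routine modelling and reliance on model assumptions, which the retained Wilcoxon helps to check. No new data are needed.
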